## 6.2. Trial Endpoints

### 6.2.1. Primary Endpoints

The *primary safety endpoint* is the incidence and severity of all treatment-emergent adverse events from baseline through Month 12.

The *primary efficacy endpoint* is change from baseline at the Month 12 timepoint in functional capacity as assessed by the full PUL 2.0 (high-level + mid-level + distal level dimensions).

### 6.2.2. Secondary Endpoints

The *secondary safety endpoint* is the incidence and severity of all treatment-emergent adverse events from baseline through Month 60.

The *secondary efficacy endpoints* include the changes from baseline through the Month 60 timepoint for the following:

- Upper body functionality using PUL 2.0 assessment at Months 12, 24, 36, 48, and 60
- Distal-level PUL 2.0 for subgroup of subjects with entry level scores of 2 and 3 at Months 12, 24, 36, 48, and 60
- Mid-level PUL 2.0 for subgroup of subjects with entry level scores of 4 and 5 at Months 12, 24, 36, 48, and 60
- Left Ventricular Ejection Fraction (LVEF) (i.e., Cardiac MRI) measurement at Month 24, 36, 48, and 60
- Left Ventricular End Systolic Volumes-Indexed (ESVI) measurement at Month 24, 36, 48, and 60
- Left Ventricular End Diastolic Volumes-Indexed (EDVI) measurement at Month 24, Month 36, 48, and 60
- Other cardiac parameters, including but not limited to mass, unindexed volumes, cardiac output, wall thickening percentage, and end diastolic and end systolic wall thickness at 24, 36, 48, and 60

## 6.2.3. Exploratory Endpoints

The *exploratory efficacy endpoints* include the retrospective standard-of-care patient data from HOPE-2 to the beginning of HOPE-2-OLE and/or an external comparator pertaining to the following at appropriate timepoints:

- Upper body functionality (i.e., PUL 2.0)
- Left ventricular Ejection fraction (LVEF) (i.e., cardiac MRI)

Exploratory safety endpoints include the analysis of the elevation of HLA antibodies against the donor cells (i.e., DSAs) to determine a level considered clinically significant using mean florescence intensity [MFI].

## 6.3. Number of Subjects

Up to 16 subjects will be enrolled.

## 6.4. Deramiocel Treatment

All subjects will receive open-label deramiocel (150M CDCs) administered as an intravenous infusion on Day 1 and Months 3, 6, 9, 12, 15, 18, 21, 24, 27, 30, 33, 36, 39, 42, 45, 48, 51, 54, and 57.

# 6.5. Dose Adjustment Criteria

There are no planned dose adjustments. Should an acute toxicity arise during the infusion (e.g., hypersensitivity reaction, pulmonary decompensation, etc.), the infusion should be terminated immediately, and the actual total dose administered recorded. Any decision about re-challenging in a subsequent infusion should be made after discussions with the Investigator, Medical Monitor, Data Safety Monitoring Board (DSMB), and other medical experts that may be required to make an informed decision.

## 6.6. Criteria for Trial Termination

The trial may be terminated at any time and for any reason, including, but not limited to, a recommendation by the DSMB for safety reasons, an action by the FDA, or decision by Capricor.

# 7. SELECTION AND WITHDRAWAL OF SUBJECTS

Subjects who meet all inclusion criteria and no exclusion criteria will be eligible for the trial.

# 7.1. Subject Inclusion Criteria

Inclusion criteria will be assessed within 30 days prior to first infusion on Day 1 unless otherwise noted:

- 1. Documented enrollment in the HOPE-2 trial and completion of trial follow-up through Month 12
- 2. Willing and able to provide informed consent to participate in the trial if  $\geq 18$  years of age, and assent with parental or guardian informed consent if < 18 years of age
- 3. Adequate venous access for intravenous deramiocel infusions in the judgement of the Investigator
- 4. Assessed by the Investigator as willing and able to comply with the requirements of the trial

# 7.2. Subject Exclusion Criteria

Exclusion criteria will be assessed within 30 days prior to first infusion on Day 1 unless otherwise indicated:

- 1. Planned or likely major surgery in the next 12 months after planned first infusion
- Risk of near-term respiratory decompensation in the judgment of the investigator, *or* the need for initiation of non-invasive ventilator support as defined by serum bicarbonate ≥ 29 mmol/L
- 3. History of non DMD-related chronic respiratory disease including, but not limited to, asthma, bronchitis, and tuberculosis
- 4. Acute respiratory illness within 60 days prior to first infusion
- 5. Known allergy or hypersensitivity to any of the IP constituents such as dimethyl sulfoxide (DMSO) or bovine proteins
- 6. Treatment with an investigational product  $\leq 6$  months prior to first infusion
- 7. History, or current use, of drugs or alcohol that could impair ability to comply with participation in the trial
- 8. Inability to comply with the investigational plan and follow-up visit schedule for any reason, in the judgment of the investigator

# 7.3. Screen Failures

Any subject who provides written informed consent/assent and is ultimately not infused for whatever reason will be classified as a screen failure. Screen failures will be recorded on a trial

log outside of the clinical database and submitted at the end of the trial to Capricor. Please reference the Manual of Operations for further information on capturing screen failure data.

# 7.4. Subject Withdrawal Criteria

Every effort will be made to have each subject complete all elements of the trial. If a subject has started at least one IP infusion and withdraws prior to trial completion, all attempts must be made to perform the trial assessments indicated for Month 60 visit.

Criteria for withdrawal from trial participation include the following reasons:

- A subject may withdraw his consent at any time without prejudice to his care.
- At the discretion of the Investigator, the subject may be withdrawn from the trial for lack of adherence to the investigational plan.
- A subject may be withdrawn from the trial for an acute reaction to deramiocel or other safety issue that prevents repeat infusions. In this instance, the subject should be followed on trial for at least 3 months after the last deramiocel infusion and then complete the Month 60 visit.

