## 10.2.4. Reporting Adverse Events

All adverse events are collected from the time of signing informed consent for trial participation until completion of the Month 60 visit or early termination, whichever occurs first. All AEs occurring after the initiation of the IV catheter placement for the initial dose of deramiocel will be considered treatment emergent. Any ongoing adverse event that has not been resolved at the time of trial completion or early termination for a subject will be marked as ongoing on the adverse event case report form (CRF).

All AEs will be entered into the electronic data capture (EDC) system by trained site personnel at the investigative site.

Expected and unexpected SAEs must be reported to Capricor and entered into the EDC system within 24 hours of discovery of the event. For events that do not have complete information available at the time of initial report, the investigative site will submit all available information at the time of the submission. All SAE Report Forms must be signed by an Investigator and submitted with available source documentation. All source documentation must be de-identified prior to submission.

All SAEs must be reported to the respective IRB in accordance with the investigative site's policies. Copies of the submission will be collected by Capricor.

All SAEs will be reported to the DSMB at least semi-annually, or more frequently at the discretion of the Medical Monitor.

Capricor will promptly upon discovery, report serious and unexpected adverse events for which there is a reasonable possibility that the investigative therapy (i.e. administration product and/or investigative product) caused the events, to the Food and Drug Administration (FDA) in accordance with 21 CFR 312.32 regulations and ICH E2A guidelines.

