#### 10.2.6. Adverse Event Follow-up

All AEs are followed by the investigative site until an outcome is known or the subject's participation in the trial concludes at either the Month 60 visit or early termination, whichever occurs first.

The investigative site is expected to review all ongoing AEs at each visit. AEs are followed until resolution or until no further changes in the event are expected (i.e., the point at which a subject experiencing an AE is treated successfully and stabilized even though he may continue to experience lingering sequelae that may never resolve), or it is agreed that further follow-up of the event is not warranted (e.g., non-serious, IP unrelated, ongoing at final visit). See Section 10.2.3 for reporting ongoing AEs at the end of trial participation.

For SAEs that were incomplete or ongoing at the time of initial submission, the investigative site is required to submit follow-up SAE Report Forms when event information is available to the research site personnel and/or an outcome is known.

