## APPENDIX A. TRIAL DESIGN

Month 54 Infusion #19

Procedure / Event	Screening 	Baseline  / Day 1	Month 3	Month 6	Month 9	Month 12	Month 15	Month 18	Month 21	Month 24	Month 27	Month 30	Month 33	Month 36	Month 39	Month 42	Month 45	Month 48	Month 51, 54, 57	Month 60 Or Early Term
Trial Day (Visit Window)	≤ 30 d prior to Day 1	1 d	(±14)	(±14)	(±14)	(±14)	(±21)	(±21)	(±21)	(±21)	(±21)	(±21)	(±21)	(±21)	(±21)	(±21)	(±21)	(±21)	(±21)	(±21)
Intravenous Infusion #		#1	#2	#3	#4	#5	#6	#7	#8	#9	#1 0	#11	#12	#13	#14	#15	#16	#17	#18, 19 20	
Informed Consent / Assent	x					x				х				x						
Demographics	x																			
Medical History 	х																			
Eligibility Assessment	x																			
Pre-Treatment Medications		x	x	х	х	х	х	x	х	х	х	x	x	х	х	х	х	х	х	
Adverse Events 	x	x	x	х	х	х	х	х	х	х	х	x	х	х	х	х	х	х	х	x
Deramiocel (CAP-1002) Infusion 		x	x	х	х	х	х	x	х	х	x	x	x	х	х	х	x	х	x	
Vital Signs	x	х	x	х	х	х	х	х	х	х	x	x	x	х	х	х	х	х	х	x
Ulna Length 	x	x	x	х	х	х	х	х	х	х	х	x	х	х	х	х	х	х	х	x
Weight	х	х	х	х	х	х	х	х	х	х	х	x	х	х	х	х	х	х	х	x
Physical Examination	х	х	х	х	х	х	х	х	х	х	х	х	х	х	х	х	х	х	х	х
Serum chemistry 										х				х				х		х
Hematology 										х				х				х		x
DSA 										Х				х				Х		x
Coagulation Panel 																		X 	X 	
PUL 2.0		X	x	Х	Х	Х	Х	Х	Х	Х	Х	X	Х	Х	Х	Х	Х	Х	Х	X
Cardiac MRI	Standard-of-Care					X 				X 				X 		X 				

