## APPENDIX B. SCHEDULE OF ASSESSMENTS

Page 72 of 78 Capricor, Inc. - Company Confidential

-  Some screening assessments may be conducted via telephone, but in-person assessments must be conducted prior to Baseline infusion.
-  Baseline safety and efficacy assessments will be conducted prior to infusion on Day 1. Every effort should be made to have each subject complete all elements of the trial.
-  If a subject has started at least one deramiocel infusion and withdraws prior to trial completion, all attempts must be made to perform a final comprehensive visit.
-  Medical histories will be assessed for upper body functionality (i.e., PUL 2.0) and Left Ventricular Ejection Fraction (i.e., cardiac MRI). The assessment periods will cover the time from the end of HOPE-2 to the beginning of HOPE-2-OLE.
-  A blood sample for tryptase should be obtained within 3 hours of the onset of allergic signs and symptoms and analyzed locally.
-  All deramiocel infusions will be conducted in an outpatient setting at the investigative site. It occurs every 3 months anchored from the previous infusion for a total of up to 20 infusions (Day 1, Month 3, Month 6, Month 9, Month 12, Month 15, Month 18, Month 21, Month 24, Month 27, Month 30, Month 33, Month 36, Month 39, Month 42, Month 45, Month 48, Month 51, Month 54, and Month 57). Prior to each deramiocel infusion, medications will be administered to the subject as determined by the Investigator based on pre-treatment guidelines provided by Capricor and/or institutional protocols to minimize risk of potential severe allergic reactions such as anaphylaxis. Subjects will be observed for at least 2 hours post-infusion, including pulse oximetry monitoring for at least 30 minutes post-infusion. Sites will observe institutional policies related to parenteral infusions and post-infusion monitoring.

 Ulna length will be measured in all subjects and height will be calculated using a measurement of ulna length.

 Blood samples will be collected using trial-specific laboratory kits and then shipped to and tested at a central or local laboratory. Required sample collection for a visit may occur on multiple days; if the visit includes an IP infusion, sample collections should occur prior to IP administration.

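### After a safety stop of infusions, Protocol 7.4 may close adverse-event collection at an exit visit, while SAP 7.1 reports crude percentages to Month 60

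*Protocol*

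**What the plan says.** **Withdrawal.** Protocol 7.4 names an acute reaction, or another safety issue that prevents repeat infusions, among the criteria for withdrawal from trial participation. Withdrawal is permitted, not required. For such a subject, "the subject should be followed on trial for at least 3 months after the last deramiocel infusion and then complete the Month 60 visit". The timing of that last visit is not given.

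**The exit visit.** Earlier in 7.4, for any subject who has started an infusion and then withdraws, "all attempts must be made to perform the trial assessments indicated for Month 60 visit". The schedule of assessments has one shared column, "Month 60 Or Early Term". Its footnote 3 says that if a dosed subject "withdraws prior to trial completion, all attempts must be made to perform a final comprehensive visit".

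**End of collection.** Protocol 10.2.4 collects adverse events "until completion of the Month 60 visit or early termination, whichever occurs first". Under 10.2.6 they are followed until the outcome is known or the subject's "participation in the trial concludes at either the Month 60 visit or early termination, whichever occurs first".

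**Definition and endpoint.** Under 10.2.4, "All AEs occurring after the initiation of the IV catheter placement for the initial dose of deramiocel will be considered treatment emergent". This has a start but no end tied to the last infusion. The secondary safety endpoint (Protocol 6.2.2) is "the incidence and severity of all treatment-emergent adverse events from baseline through Month 60".

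**Analysis.** SAP 7.1 gives numbers and percentages of subjects with an event, plus event counts, first for 12 and then for 60 months. The population is everyone who received any product (SAP 4.6). Neither document plans a subject-time denominator or a time-to-event summary for adverse events.

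**The concern.** Stopping the product and leaving the trial are treated as one event. If the Month 60 visit is an exit visit, safety observation of a subject who cannot tolerate the product can end 3 months after his last infusion. He still counts as a full subject in a percentage labelled as running to Month 60. The reaction that caused the exit is recorded; anything after the exit is not. Follow-up is then shortest in those who reacted to the product, and the table does not show it. The secondary safety endpoint is the one exposed. The 12-month primary safety window is affected only when the last infusion comes before Month 9.

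**Working it through.** The plan gives no expected event rate, power or sample-size figure on this point, so there is nothing of its own to reproduce. The check has a textual part and an illustrative calculation.

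**1. Which visit is meant?** Two readings are possible.
- *Exit visit.* Supported by the general withdrawal sentence in 7.4, which asks for the Month 60 assessments on withdrawal; by the shared schedule column; and by footnote 3, which gives no calendar time. The safety-stop sentence also sits in a list of reasons for leaving the trial.
- *Calendar Month 60.* The words allow it, and the subject would then still be on trial until that date.

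The text favours the exit reading but does not settle it. Under the exit reading, 10.2.4 and 10.2.6 close collection at that visit. Under the calendar reading, collection runs to Month 60 and no events are lost.

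**2. Size under the exit reading.** Inputs:
- N = 13 (SAP 3.1 and 4.1). Protocol 6.3 and 13.2 allow up to 16.
- Window of 60 months (Protocol 6.2.2).
- Earliest exit at Month 3: last infusion on Day 1 plus the 3-month floor.
- Assumed: incidence F over 60 months, the same constant hazard in all subjects that continues after infusions stop, and k leavers at month t.

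Expected crude percentage = [(13 − k) × F + k × (1 − (1 − F)^(t/60))] / 13.

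For F = 20% and k = 1:

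| Exit month | Leaver's chance of a recorded event | Expected crude % | Subjects missed |
|---|---|---|---|
| 3 | 1 − 0.8^0.05 = 0.011 | (2.4 + 0.011)/13 = 18.5 | 0.19 |
| 30 | 1 − 0.8^0.5 = 0.106 | (2.4 + 0.106)/13 = 19.3 | 0.09 |
| 54 | 1 − 0.8^0.9 = 0.182 | (2.4 + 0.182)/13 = 19.9 | 0.02 |

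The largest loss for one leaver is 0.189/13 = 1.45 points, or 0.189/16 = 1.18 points with 16 subjects. The loss is proportional to k: two leavers at Month 3 lose 2 × 1.45 = 2.9 points.

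Over incidences of 10% to 60%, the relative loss for one leaver is 7.1% to 7.3% at Month 3 and 3.0% to 3.7% at Month 30. At 60% incidence and exit at Month 3, 7.1% of 60 is about 4.3 points.

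**3. The same event as a rate.** Hazard = −ln(0.8)/60 per month = 4.46 per 100 subject-years. A subject followed to time t has expected first events 1 − e^(−λt) and expected time at risk (1 − e^(−λt))/λ. The ratio is λ for any t, so the rate stays at 4.46 whoever leaves and when. This rests on the constant, common hazard.

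**4. Why two denominators.** Suppose follow-up is extended and an event occurs only on treatment, at 4.46 per 100 on-treatment subject-years. On-treatment time runs to 3 months after the last infusion, so a completer (last infusion Month 57) contributes 5 years and a subject stopped after Day 1 contributes 0.25.
- One early stopper: on-treatment time 12 × 5 + 0.25 = 60.25; all observed time 13 × 5 = 65. Rate on all time: 4.46 × 60.25/65 = 4.14, which is 7.3% lower.
- Two: 11 × 5 + 2 × 0.25 = 55.5. Rate on all time: 4.46 × 55.5/65 = 3.81, which is 14.6% lower.

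Because the treatment-emergent definition has no end date, extended follow-up reported on all observed time alone would dilute infusion-related events.

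**The case against.** The harm hangs on one ambiguous phrase. Under the calendar reading it disappears. Withdrawal is optional, 3 months is a minimum, 7.4 opens by asking sites to keep every subject in the whole trial, and Protocol 6.5 provides for discussion of re-challenge. All of this stands, and it limits how often the problem can arise. It does not tell a site which visit is meant.

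The size is also small. One subject in 13 is 7.7 points, so a loss of 1.5 points is below the table's resolution; an observed 3/13 (23%) has an exact 95% interval of about 5% to 54%. That stands too, and it is why this is a suggested improvement rather than a defect that undermines the trial.

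The two calculations assume different things. Step 2 lets the hazard continue off treatment; step 4 confines it to treatment. Under the second assumption, longer follow-up finds no further events and an exit misses none. This also stands: the understatement applies only to events that can still occur off treatment.

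The AE listings, infusion details (SAP 5.8), visit dates (SAP 5.9) and disposition (SAP 5.10) would let a reader work out subject-time. That is true, but the work is left to the reader.

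Three stronger inferences are tempting, and the documents do not support them:
- *The protocol cuts safety follow-up at 3 months.* It sets a floor and leaves the final visit undated.
- *Interim visits lapse under either reading.* No passage waives scheduled visits for a subject still on trial, and 10.2.6 expects ongoing events to be reviewed at each visit.
- *Efficacy results are biased as well.* Protocol 12.2 provides a cardiac MRI at early termination, the SAP 6.4 mixed model keeps a leaver's earlier data, and the waning described in 4.7.1 concerns PUL 1.2 only. No direction of bias follows.

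**Conclusion.** The point holds in a limited form. Protocol 7.4 merges stopping infusions with leaving the trial and does not date the Month 60 visit. On the better-supported reading, adverse-event collection ends at exit while SAP 7.1 carries the subject in the denominator to Month 60. For events that can still occur off treatment, the crude 60-month percentages can then be too low, by at most about 1.5 points per leaver. That figure assumes 20% incidence, a constant and equal hazard that continues off treatment, 13 subjects and exit no earlier than Month 3; commoner events lose more points but a similar share. The number of leavers cannot be estimated from the documents, so no total is given. This is a low-cost improvement to consider.

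**What to change.** 1. **Protocol 7.4.** Separate stopping infusions from leaving the trial, and state that the Month 60 visit means calendar Month 60 for a subject who stops for safety. For subjects who have not withdrawn consent, continue adverse-event collection to that date at existing visits or by telephone. Who stops infusions, and when, does not change.
2. **SAP 7.1.** Beside the crude percentages, add treatment-emergent event rates per subject-year for two periods: on-treatment time, to 3 months after the last infusion, and all observed time.

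The cost is a short amendment with IRB review, a few off-treatment contacts that some subjects may decline, and one or two extra table columns. The amendment acts only forward: if it took effect at Month 36 or 48 (assumed), it would add at most 60 − 36 = 24 or 60 − 48 = 12 months per leaver. The SAP rates use data already collected and are worth adding even if 7.4 is left as it is.

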# 8. TREATMENT OF SUBJECTS

## 8.1. Description of Investigational Product

Deramiocel is provided in units per vial of 75 million CDCs in a cryogenic cell preservation solution. Two units of deramiocel comprise a single dose of 150 million CDCs for intravenous infusion.

Please see Section 9 for more information on investigational product.

## 8.2. Concomitant Medications

Refer to exclusion criteria for medications / therapies that exclude a subject from trial participation.

All efforts should be made to maintain the same DMD medication regimen throughout the course of the trial. This should be discussed with the subject's primary medical doctor and caregivers at the outset of the trial and during the trial follow-up period.

Capricor requires treatment of subjects prior to each infusion, as outlined in Section 9.7, to minimize the risk of a potential severe hypersensitivity reaction.

### 8.2.1. Permitted concomitant medications changes

Agamree® (vamorolone) has been approved by FDA as a steroidal anti-inflammatory agent. Patients may switch standard-of-care steroid therapy to vamorolone provided that the following conditions are met:

- Current steroid regimen must be administered daily. There is no data available as to the equivalency of non-daily (i.e., weekend, once a week, etc.) dosing of corticosteroids to vamorolone. Such participants on non-daily dosing may not be allowed to switch to vamorolone while on-study.
- Participants on daily dosing of corticosteroids may switch to an equivalent dose of vamorolone after the Month 12 visit at a maximum dose of 6.0 mg/kg, but not less than 2.0 mg/kg and not to exceed a total daily dose of 300 mg.
- Guidance for prednisone/deflazacort conversion is as follows:
  - Prednisone 0.75 mg/kg/day = Vamorolone 6.0 mg/kg/day
  - Deflazacort 0.9 mg = Prednisone 0.75 mg

Page 35 of 78 Capricor, Inc. - Company Confidential

- All other prescribing information considerations per the package insert must be followed (https://www.accessdata.fda.gov/spl/data/2a128ee3-956f-49eb-aa4e-9691bb4c1b5d/2a128ee3-956f-49eb-aa4e-9691bb4c1b5d.xml)
- Any switch to vamorolone dosing while on study must be approved by Capricor prior to making the switch.
- The switch cannot occur within 2 weeks of any given infusion.
- If the vamorolone dose cannot be tolerated, the patient may resume his original corticosteroid medication and dose.

